12.3 Statistical Analyses

12.3.1 Primary endpoint

The primary endpoint is defined as the absolute change in BPI worst pain from baseline to 15 weeks. This change will be reported with the corresponding 95% confidence interval. Differences from baseline at each time point for worst pain will be summarized via mean and standard deviation. Patient reported outcomes will be analyzed using linear mixed effects models and include a subject-specific random effect to account for the natural heterogeneity across patients. Normalizing transformations will be used if necessary to ensure accurate model fit.

12.3.2 Secondary endpoints

- 1. The proportion of patients who have at least a 2 point reduction in *worst* pain from baseline to 15 weeks will be reported with the corresponding exact binomial confidence interval.
- 2. The proportion of patients who have at least a 2 point reduction in *average* pain from baseline to 15 weeks will be reported with the corresponding exact binomial confidence interval. Differences from baseline at each time point for average pain and pain interference will be summarized via mean and standard deviation. Patient reported outcomes will be analyzed using linear mixed effects models and include a subject-specific random effect to account for the natural heterogeneity across patients. Normalizing transformations will be used if necessary to ensure accurate model fit.
- 3. Differences from baseline at each time point for all other patient reported outcomes (sleep disturbance, fatigue, physical function, anxiety, depression, and cognitive function over time) will be summarized via mean and standard deviation. Patient reported outcomes will be analyzed using linear mixed effects models and include a subject-specific random effect to account for the natural heterogeneity across patients. Normalizing transformations will be used if necessary to ensure accurate model fit.
- 4. Safety will be assessed throughout the trial and adverse events will be reported using descriptive statistics and stratified by dose.
- 5. We will report the proportion of individuals with undetectable levels of estradiol at baseline and 15 weeks with corresponding exact binomial 95% confidence intervals. The exact levels of estradiol at baseline and 15 weeks will be summarized using descriptive statistics.

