4.2 Number of Patients

A total of 44 patients will be enrolled, assuming a 10% dropout rate, for a total of 40 evaluable patients. Patients who discontinue trial participation prior to initiating CBD therapy will be replaced.

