7.1.2 Preparation and Administration

Patients should be instructed to take 25 mg (0.25 ml) twice a day approximately 12 hours apart for the first week, with food. Each week the patient should increase the dose by 25 mg twice a day until she reaches a maximum of 100 mg (1 ml) twice a day, unless she has difficulty tolerating the medication. If a dose is missed the patient should take it as soon as she remembers, although if it has been more than 8 hours she should not double up on dosing. If a dose is vomited it should not be made up.

The drug should be drawn up into a dry syringe. If the syringe is wet, it can make the drug appear cloudy; this does not affect its safety or efficacy.

Patients will be advised not to drive or operate machinery until they have gained sufficient experience on the study drug to gauge whether it adversely affects their ability to drive or operate machinery. Participants will be advised that concomitant use of alcohol or other CNS depressants may increase sedation and somnolence.

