7.2.2 Prohibited Therapy

Patients with a history of hormone receptor positive breast cancer should avoid taking systemic or transdermal estrogen products (vaginal estrogen preparations are permitted).

Patients should not take valproate or clobazam while participating on this clinical trial.

7.3 **Duration of Therapy**

Patients will be treated with the study drug for 15 weeks (+/- 7 days).

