8.1 Dose Modifications and Guidelines for Adverse Event Management

8.1.1 Dose Modifications

Dose levels:

- Dose level 1 25 mg BID
- Dose level 2 50 mg BID
- Dose level 3 75 mg BID
- Dose level 4 100 mg BID

If the dose is reduced because of toxicity, that dose should be maintained for the remainder of the trial and not re-escalated.

Toxicity Grade	What to do
Grade 1 – possibly, probably, or definitely related to study drug	For ALT/AST > 3x ULN, discontinue study medication.
	For all other grade 1 toxicities, monitor as needed until the problem has resolved (i.e., grade 0), stabilized (i.e., remains as grade 1), or is otherwise explained.
	If Grade 1 symptoms persist, the PI or Co-I will assess whether the dose should be reduced by 1 dose level or, if the patient is receiving dose level 1, whether the patient should discontinue study medication.
Grade 2 – possibly, probably, or definitely related to study drug	For total bilirubin > 2x ULN, discontinue study medication.
	For all other grade 2 toxicities, monitor as needed until the problem has resolved (i.e., grade 0), stabilized (i.e., remains as grade 1 or grade 2), or is otherwise explained.
	If Grade 2 symptoms persist, the PI or Co-I will assess whether the dose should be reduced by 1 dose level or, if the patient is receiving dose level 1, whether the patient should discontinue study medication.
Grade 3 – possibly, probably, or definitely related to study drug	If the patient was receiving dose level 1 at the time of toxicity development, the patient should discontinue study drug.
	For patients receiving dose level 2 or higher, if the symptoms resolve or improve to grade 1 or 2 within 7 days, the dose should be reduced by 1 dose level and the drug restarted at the time of symptom improvement. This dose is to be maintained if no further Grade 3 toxicity is noted.
	If the symptoms do not resolve or improve to grade 1 or 2 within 7 days, the patient can continue to hold study drug for another 7 days. If the symptoms resolve or improve to grade 1 or 2, the dose should be reduced by 1 dose level and the drug restarted at the time of symptom improvement. This dose is to be maintained if no further Grade 3 toxicity is noted. If

	the symptoms remain Grade 3 possibly, probably, or definitely related to the study drug, the patient should be permanently removed from protocol treatment.

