16.5.2 Adverse Event Reporting Requirements

Adverse event (AE) monitoring and reporting is a routine part of every clinical trial and is done to ensure the safety of subjects enrolled in the studies as well as those who will enroll in future studies using similar agents. Data on adverse events will be collected from the time of the initial study treatment through 30 days after the last dose of study treatment. Any serious adverse event that occurs more than 30 days after the last study treatment and is considered related to the study treatment must also be reported. Serious Adverse Events (SAEs) will continue to be followed until:

- Resolution or the symptoms or signs that constitute the serious adverse event return to baseline;
- There is satisfactory explanation other than the study treatment for the changes observed; or
- Death.

The investigator is responsible for the detection, documentation, grading and assignment of attribution of events meeting the criteria and definition of an AE or SAE. The definitions of AEs and SAEs are given below. It is the responsibility of the principal investigator to ensure that all staff involved in the trial is familiar with the content of this section.

Any medical condition or laboratory abnormality with an onset date before initial study treatment administration is considered to be pre-existing in nature. Any known pre-existing conditions that are ongoing at time of study entry should be considered medical history.

All events meeting the criteria and definition of an AE or SAE, as defined in Section 8.3, occurring from the initial study treatment administration through 30 days following the last dose of the study treatment must be recorded as an adverse event in the patient's source documents and on the CRF regardless of frequency, severity (grade) or assessed relationship to the study treatment.

In addition to new events, any increase in the frequency or severity (i.e., toxicity grade) of a pre-existing condition that occurs after the patient begins study treatment is also considered an adverse event.

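### Adverse events are to be stratified by dose with no definition of dose and no denominator; under the planned titration a crude by-dose table can show a false dose pattern

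*Combined protocol and SAP*

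**What the plan says.** Safety and tolerability of 15 weeks of CBD is the third secondary objective (section 1.2). The statistical plan for adverse events is one sentence in section 12.3.2, Secondary endpoints, item 4: they "adverse events will be reported using descriptive statistics and stratified by dose". Section 11.1 adds that safety is judged from reported signs and symptoms and from laboratory results. Neither these sections nor sections 16.5.2 to 16.5.6 mention time at each dose, patients at risk, or a rule that links an event to a dose.

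Dose changes within patients. Section 7.1.2 has patients "take 25 mg (0.25 ml) twice a day approximately 12 hours apart for the first week", and then: "Each week the patient should increase the dose by 25 mg twice a day until she reaches a maximum of 100 mg" twice a day, unless tolerability prevents it. The ceiling is the last of four levels in section 8.1.1 ("Dose level 4 100 mg BID"). Section 7.3 sets 15 weeks of treatment, give or take 7 days. Section 8.1.1 also states: "If the dose is reduced because of toxicity, that dose should be maintained for the remainder of the trial and not re-escalated". Section 16.5.2 collects adverse events "from the time of the initial study treatment through 30 days after the last dose", so part of the collection window is off drug. On numbers, section 4.2 says: "A total of 44 patients will be enrolled, assuming a 10% dropout rate, for a total of 40 evaluable patients".

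**The concern.** A table by dose invites the reader to compare columns. Here the columns are not parallel groups. They are stages that the same patients pass through in a fixed order, with very unequal time in each, and the plan leaves open how an event is placed in a column.

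- **Dose at onset.** Crude counts then largely reflect how long patients spent at each level and how events are distributed over time.
- **Final dose.** Patients who could not escalate, or who were reduced for toxicity and kept at the lower level, make up the low-dose groups. Low doses could then look more toxic because of who is in those groups.

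Either reading can mislead about dose and tolerability. Because the choice is not fixed in advance, it could be made after the data are seen.

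**Working it through.** **Plan's own figure.** The documents give no exposure time per level, so there is no stated figure to reproduce. The exposure below is counted from the titration rule.

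**Step 1: time at each level under full titration.** Weeks 1, 2 and 3 are at 25, 50 and 75 mg BID, and weeks 4 to 15 are at 100 mg BID. That is 1, 1, 1 and 12 weeks, or 7, 7, 7 and 84 of 105 days. Level 4 has 84/105 = 80% of treatment time and each lower level 7/105 = 6.7%. At 14 or 16 weeks of treatment, level 4 has 14 − 3 = 11 or 16 − 3 = 13 weeks.

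*Cross-check against drug supply (section 7.1.1: 100 mL at baseline and 100 mL at week 8).* At 14 doses a week and 100 mg/mL, weeks 1 to 8 need 3.5 + 7 + 10.5 + 5 × 14 = 91 mL, and weeks 9 to 15 need 7 × 14 = 98 mL. Each fits one bottle, so the supply agrees with this reading of the schedule.

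**Step 2: constant rate, no dose effect.** For 44 fully titrated patients, patient-weeks are 44, 44, 44 and 44 × 12 = 528. The event rate is an assumption, since the documents give none; the range used is 0.01 to 0.10 new events per patient-week. Expected events = rate × patient-weeks. Probability of at least one event = 1 − exp(−rate × weeks).

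| Assumed rate per patient-week | Events at each of levels 1–3 | Events at level 4 | Patients with an event, each of levels 1–3 | Patients with an event, level 4 | Ratio by patients |
|---|---|---|---|---|---|
| 0.01 | 0.44 | 5.28 | 1.0% | 11.3% | 11.4 |
| 0.05 | 2.2 | 26.4 | 4.9% | 45.1% | 9.3 |
| 0.10 | 4.4 | 52.8 | 9.5% | 69.9% | 7.3 |

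The ratio of event counts is 528/44 = 12 at every rate. Divided by patient-weeks, all four levels show the same rate and the gradient disappears.

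**Step 3: events that cluster early, still no dose effect.** Let the rate halve every h weeks. Events at level 1 are proportional to 1 − 2^(−1/h), and at level 4 to 2^(−3/h) − 2^(−15/h).

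| h (weeks) | Level 1 | Level 4 | Count ratio, level 4 to level 1 | Ratio per patient-week (divide by 12) |
|---|---|---|---|---|
| 1 | 0.500 | 0.125 | 0.25 | 0.02 |
| 2 | 0.293 | 0.348 | 1.19 | 0.10 |
| 4 | 0.159 | 0.520 | 3.27 | 0.27 |

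The crude pattern can therefore rise, vanish or reverse with no dose effect at all. The last column shows that patient-week rates do not separate dose from time on drug either.

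**Step 4: departures from full titration.** If, as an assumption, 25% of patients stayed at level 2 from week 2, patient-weeks would be 44; 44 × (0.75 × 1 + 0.25 × 14) = 187; 44 × 0.75 = 33; and 44 × 0.75 × 12 = 396. Exposure is still uneven, in a different shape.

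**Step 5: the off-drug window.** If events in the 30 days after the last dose were credited to level 4, it would have 12 + 30/7 = 16.3 of 19.3 weeks, or 84%.

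**Step 6: other things that move with dose.** Coordinator calls, which assess adverse events, fall at weeks 1, 2, 3, 4, 6, 8, 12 and 15 (section 9). Three of eight (37.5%) are in weeks 1 to 3, against 3/15 = 20% of treatment time. The plasma half-life is 56 to 61 hours (section 3.1.4, Pharmacokinetics). Five half-lives are 280/24 = 11.7 to 305/24 = 12.7 days, longer than a one-week step, so exposure carries over between levels.

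**The case against.** The strongest reply is that this is a gap in wording. The plan says descriptive statistics; it does not say crude counts, and it does not rule out rates or person-time. **This stands.** A reader might infer that the sponsor has decided against exposure adjustment, but the documents are only silent.

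A reader might also infer that every patient spends 12 weeks at the top dose and that the published table will show a 12-fold gradient. The documents do not support this. Section 7.1.2 allows non-escalation, section 8.1.1 lasting reductions and section 7.3.1 discontinuation, and section 12.2 expects 10% to discontinue. No time course of events is given, and Step 3 shows that the gradient can shrink or reverse.

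It is also fair to say that patient-week rates can replace one false pattern with another, and that denser early contact could inflate the rates at low doses. This limits what the remedy can do. It is a reason for a stated caveat and a display by study week, and it does not rescue the crude table.

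Finally, the trial has no dose-finding objective, no hypothesis test on adverse events and no stopping rule tied to this table. Section 11.1 also brings laboratory results into the safety evaluation, so the by-dose table is not the whole of it. This limits the importance of the point. It does not remove it, because stratification by dose is what the plan commits to and both natural readings of it can mislead.

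**Conclusion.** The point holds in a limited form. Stratification by dose is specified without a definition of dose or a denominator, in a design where the planned titration ties dose to time on drug. With full titration and a constant, dose-independent rate, level 4 would collect 12 times the events of each lower level, or 7.3 to 11.4 times by patients with an event at the assumed rates. That is one scenario and not a forecast: with rates halving every 1, 2 or 4 weeks, the count ratio is 0.25, 1.19 or 3.27. Grouping by final dose gives a different bias, through selection for intolerance. The supported conclusion is that the table can mislead about dose, in a direction that cannot be known in advance. This is a descriptive secondary endpoint in a single-arm trial, so the change is a cheap improvement. The primary endpoint is not affected.

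**What to change.** Amend item 4 of the secondary endpoints in section 12.3.2 as follows.

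1. Make overall adverse event incidence in all treated patients, not split by dose, the main safety result.
2. Define dose as the dose level at event onset.
3. For each level, report patients at risk, patient-weeks, and events per patient-week with a 95% confidence interval. Show the same by study week.
4. Give events with onset after the last dose their own row.
5. State that by-dose comparisons are descriptive, because titration confounds dose with time on drug, contact frequency and carry-over.

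**Cost.** No change to dosing, visits or sample size; a little extra tabulation. Dates of dose changes must be captured. The drug diary (section 7.1.3) and the coordinator calls (section 9) are the natural sources, but the documents do not state that either records these dates, so this should be checked.

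Rates for levels 1 to 3 will be imprecise. For example, 2 events in 44 patient-weeks is 4.5 per 100 patient-weeks. The exact Poisson 95% limits are half the 2.5% chi-square point on 4 df (0.484/2 = 0.242 events) and half the 97.5% point on 6 df (14.449/2 = 7.225 events), which is 0.6 to 16.4 per 100 patient-weeks. That width should be visible to the reader.

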12.3 Statistical Analyses	
13 REGISTRATION GUIDELINES	
14 DATA SUBMISSION SCHEDULE	27
15 SPECIAL INSTRUCTIONS	27

15.1	Patient-reported questionnaires	27
15.2	Correlative Studies	
16 ETHI	CAL AND REGULATORY CONSIDERATIONS	29
16.1	Informed consent	29
16.2	Human Subjects Protections	29
16.3	Institutional Review	
16.4	Data and Safety Monitoring Plan	29
16.5	ADVERSE EVENTS	30
16.5.1	Experimental Therapy	30
16.5.3	Definitions	31
16.5.4	Adverse Event Characteristics	33
16.5.7	Reporting of Unanticipated Problems	34
16.6	Reporting of Pregnancy	34
16.7	Protocol Amendments	35
16.8	Protocol Deviations	
16.9	Food and Drug Administration (FDA)	35
16.10	Clinical Trials Data Bank	35
17 REFE	ERENCES	35

ABBREVIATIONS

[figure not shown]
AI	Aromatase inhibitor
AIMSS	Aromatase inhibitor-associated musculoskeletal symptoms
BPI	Brief Pain Inventory
CBD	Cannabidiol
CNS	Central nervous system
DSMC	Data and Safety Monitoring Committee
ER	Estrogen receptor
GRC	Global Ratings of Change
HR	Hormone receptor
IRB	Institutional Review Board
LHRH	Luteinizing Hormone Receptor Hormone
METE	Mao Expectation of Treatment Efficacy
NSAID	Non-steroidal anti-inflammatory drugs
O-CTSU	Oncology Clinical Trial Support Unit
PANAS	Positive and Negative Affect Scale
PARP	Poly adenosine diphosphate-ribose polymerase
PR	Progesterone receptor
SAE	Serious adverse event
THC	Δ^9 -tetrahydrocannabinol

T'41-	Dhage 2 Trial of Connehidial (CDD) for		
Title	Phase 2 Trial of Cannabidiol (CBD) for Treatment of Aromatase Inhibitor-Associated		
	Arthralgias		
Short Title	CBD for AIMSS (CBD-AIM)		
Protocol Identifiers (IRB – internal)	HUM00182109		
IND number	TBD		
Phase	Phase 2		
Design	Single arm phase II interventional trial		
Study Duration	2.5 years		
Study Center(s)	Single-center		
Objectives	Primary Objective:		
	To determine the effect of 15 weeks of CBD on AI-associated worst joint pain, as assessed with the Brief Pain Inventory (BPI)		
	Secondary Objectives:		
	To determine the effect of 15 weeks of CBD on other AI-associated pain symptoms, including average pain and pain interference, as assessed with the BPI		
	To determine the effect of 15 weeks of CBD on other AI-associated symptoms, including anxiety, depression, insomnia, and cognitive function, as assessed with the PROMIS-29+2 Profile		
	To examine the safety and tolerability of 15 weeks of CBD in patients with breast cancer taking aromatase inhibitor therapy		
	To examine the effect of 15 weeks of CBD on circulating estradiol concentrations		

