1.2 Secondary Objectives

- 1. To determine the effect of 15 weeks of CBD on other AI-associated pain symptoms, including average pain and pain interference, as assessed with the BPI
- To determine the effect of 15 weeks of CBD on other AI-associated symptoms, including anxiety, depression, insomnia, and cognitive function, as assessed with the PROMIS-29+2 Profile
- 3. To examine the safety and tolerability of 15 weeks of CBD in patients with breast cancer taking aromatase inhibitor therapy
- 4. To examine the effect of 15 weeks of CBD on circulating estrogen concentrations

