12.3.2 Exploratory endpoints

1. In this exploratory aim, all inflammatory markers and cytokine levels will be summarized using descriptive statistics at baseline and 15 weeks. The changes in inflammatory biomarkers will be assessed using one sample t-test of the difference (or sign test). Linear models will examine the association between the 8 and 15-week worst pain score (controlling for baseline worst pain score and change in pain worst pain) and baseline and 8 and 15-week inflammatory markers and cytokines. Normalizing transformations will be used if required.^{58, 59} We are limited in the number of covariates in each model based on sample size, so we will be careful of overfitting recognizing that patient and disease characteristics may be confounders in analysis. No correction for multiple comparisons will be applied based on the hypothesis generating nature of the aim.

2. In this exploratory aim, all questionnaire scores will be summarized using descriptive statistics at baseline and 15 weeks. The changes in survey responses will be assessed using one sample t-test of the difference (or sign test). We will use a linear model to examine the association between the 15-week worst pain severity (as measured by the BPI) and the baseline worst pain severity, and baseline and 15-week FM score. Similarly, separate models of the 15-week worst pain score will control for baseline worst pain severity and assess associations with baseline and 15-week PANAS scores and catastrophizing scores. We are limited in the number of covariates in each model based on sample size, so we will be careful of overfitting recognizing that patient and disease characteristics may be confounders in analysis. No correction for multiple comparisons will be applied based on the hypothesis generating nature of the aim.

3. We will report the proportion of individuals with undetectable levels of estrone and estrone sulfate at baseline and 15 weeks with corresponding exact binomial 95% confidence intervals. The exact levels of estrone and estrone sulfate at baseline and 15 weeks will be summarized using descriptive statistics.

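### Estradiol, a secondary objective about the effect of CBD, is analysed as two separate margins although the samples are paired; a paired analysis costs nothing

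*Combined protocol and SAP*

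**What the plan says.** The Study Summary gives the fourth secondary objective as "To examine the effect of 15 weeks of CBD on circulating estradiol concentrations". Section 1.2 words it as "To examine the effect of 15 weeks of CBD on circulating estrogen concentrations".

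Section 12.3.2 Secondary endpoints, item 5 is the whole analysis for that objective. For the binary measure: "We will report the proportion of individuals with undetectable levels of estradiol at baseline and 15 weeks with corresponding exact binomial 95% confidence intervals". For the levels: "The exact levels of estradiol at baseline and 15 weeks will be summarized using descriptive statistics". No within-patient change, cross-tabulation or interval for a difference is planned. Section 12.3.2 Exploratory endpoints, item 3 treats estrone and estrone sulfate the same way: "The exact levels of estrone and estrone sulfate at baseline and 15 weeks will be summarized using descriptive statistics".

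Elsewhere the plan does use change. Items 2 and 3 of the secondary endpoints summarise change, for example "Differences from baseline at each time point for all other patient reported outcomes". Item 1 of the exploratory endpoints reads: "The changes in inflammatory biomarkers will be assessed using one sample t-test of the difference (or sign test".

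Section 15.2.1 collects plasma at screening (or baseline), week 8 and week 15 from the same women. Section 4.2 says: "A total of 44 patients will be enrolled, assuming a 10% dropout rate, for a total of 40 evaluable patients". Section 15.2.2 lists the assay types but no detection limit.

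On safety, Section 11.1 relies on signs and symptoms together with liver tests, creatinine and hemoglobin. Item 4 of 12.3.2 Secondary endpoints names adverse events as the reported output.

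**The concern.** An effect of treatment in a single-arm trial is a within-patient change. Two proportions, each with its own binomial interval, describe two occasions. They do not use the fact that each woman is her own control. Two things are lost:

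- **Precision of the change.** It depends on how many women switch status in each direction, and the margins do not show this.
- **The count of women who become detectable.** Section 2.2 explains that aromatase inhibitors work by preventing estrogen biosynthesis, so this is the natural clinical question behind the objective. Switches in opposite directions cancel in the margins.

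Item 5 also does not restrict the two margins to women with both samples, so they may describe slightly different sets of women. A secondary objective thus gets a weaker analysis than the exploratory inflammatory markers, for which a test of change is already planned.

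**Working it through.** **Inputs.** The plan states no figure for estradiol; its power calculation (Section 12.2) concerns worst pain only. I take n = 40 from Section 4.2 (44 x 0.9 = 39.6, stated as 40). All detectability counts below are assumptions.

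**Notation.** Among n women with both samples, b go from undetectable to detectable (rises) and c the reverse (falls). The fall in the proportion undetectable is (b - c)/n. The margins fix b - c but not b + c.

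**Formulas.**
- Each margin: Clopper-Pearson exact 95% interval, as in the plan.
- Paired difference: Tango score interval, the set of d with |b - c - nd| / sqrt{n[2q + d(1 - d)]} <= 1.96. Here q = [sqrt(B^2 - 4AC) - B]/(2A), A = 2n, B = -b - c + (2n - b + c)d, C = -cd(1 - d).
- Test, if wanted: exact McNemar, a two-sided binomial test of b out of b + c against 0.5.

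**Case 1: 38/40 undetectable, then 32/40.** The planned output would be 95.0% (83.1 to 99.4) and 80.0% (64.4 to 90.9). Only 2 women are detectable at baseline, so c is 0, 1 or 2 and three tables fit:

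| Rises/falls | Fall in % undetectable | Paired 95% CI | Exact McNemar p | Newly detectable |
|---|---|---|---|---|
| 6/0 | 15.0 | 4.9 to 29.1 | 0.031 | 6/38 = 15.8% |
| 7/1 | 15.0 | 1.4 to 30.1 | 0.070 | 7/38 = 18.4% |
| 8/2 | 15.0 | -0.6 to 31.1 | 0.109 | 8/38 = 21.1% |

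The interval widens from 24.2 points (29.1 - 4.9) to 31.7 points (31.1 + 0.6). The proportion newly detectable varies little.

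**Case 2: 30/40 undetectable, then 26/40.** The planned output would be 75.0% (58.8 to 87.3) and 65.0% (48.3 to 79.4). Ten women are detectable at baseline, so c can run from 0 to 10:

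| Rises/falls | Fall in % undetectable | Paired 95% CI | Exact McNemar p | Newly detectable |
|---|---|---|---|---|
| 4/0 | 10.0 | 0.4 to 23.1 | 0.125 | 4/30 = 13.3% |
| 9/5 | 10.0 | -8.9 to 28.4 | 0.42 | 9/30 = 30.0% |
| 14/10 | 10.0 | -14.0 to 32.8 | 0.54 | 14/30 = 46.7% |

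The width roughly doubles, from 22.7 to 46.8 points. The last row is an extreme: 24 of 40 women would have to switch.

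(In the 4/0 row the score interval just excludes zero while the exact test gives p = 0.125. The two methods need not agree at such counts, so the plan should name its interval.)

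**Case 3: 32/40 at both times.** The margins show no change. The proportion newly detectable could still be 0/32 (exact 95% CI 0 to 10.9%), 4/32 = 12.5% (3.5 to 29.0) or 8/32 = 25.0% (11.5 to 43.4), the last if all 8 women detectable at baseline became undetectable.

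**The case against.** The best reply is that estradiol is meant to be descriptive. Section 1.2 uses the verb examine for this objective and determine for the pain and symptom objectives. Section 12.1 states hypotheses for pain, stiffness and anxiety only, and nothing is powered for estradiol. This stands as an answer to any demand for a formal test. It does not defend the two margins, because a two-by-two table and a paired interval are descriptive too and answer the question that the objective asks.

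A second reply is that the margins already give the net change and that undetectable is already its own category. Both are true. The net point estimate is available among women measured twice, and the proportions need no rule for censored values. Only the summary of levels does.

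Three stronger readings are tempting and are not supported:

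- A reader might infer that dropout alone could produce a large apparent shift. That would need the women lost to come almost wholly from the detectable minority, and nothing in the documents suggests this. The case for using women with both samples is comparability.
- A reader might infer that women who stop drug on a laboratory value alone would be absent from the safety results. One bullet in 16.5.3 could be read that way, but the general definition in 16.5.3 includes an abnormal laboratory finding. Section 16.5.2 treats laboratory abnormalities that begin before treatment as pre-existing, which implies that later ones are candidates. Section 8.1.1 handles the liver-test stops as graded, attributed toxicities, and 11.1 commits to evaluating the laboratory results. What stands is that 12.3 lists no laboratory summary.
- A reader might take the ranges above as forecasts. The documents give no detectability rate.

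**Conclusion.** The point holds for estradiol, and equally for estrone and estrone sulfate. As written, the plan gives a point estimate of net change but neither its paired precision nor the number of women who become detectable. With assumed counts and 40 complete pairs, identical margins fit paired intervals that differ in width by about a third (Case 1) to about two-fold (Case 2, at an extreme). If most women are undetectable at baseline, as in Case 1, the proportion newly detectable is nearly settled (16% to 21%) and the loss is mainly one of precision. With more switching, the loss is larger.

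This is worth correcting because the better analysis is free. It is a secondary, descriptive matter and does not touch the primary endpoint or the sample size. The laboratory summary is a minor addition.

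**What to change.** In 12.3.2 Secondary endpoints, item 5, among women with both a baseline (or screening) and a week-15 sample:

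1. Report the baseline by week-15 table of detectable and undetectable.
2. Report the proportion of women undetectable at baseline who become detectable, with an exact 95% interval.
3. Report the paired difference in proportions with a named paired 95% interval, such as the Tango score interval.
4. Analyse within-patient change in level by the sign method already named for the inflammatory markers. Undetectable at both times counts as no change, undetectable to detectable as a rise, and the reverse as a fall. Women detectable at both times are classed by their two values.
5. State the assay limit, and give the number and baseline status of women without a week-15 sample.

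Apply the same to estrone and estrone sulfate in 12.3.2 Exploratory endpoints, item 3.

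Minor: add to item 4 a by-visit summary of liver tests, creatinine and hemoglobin with shift from baseline. Reconcile the laboratory sentences in 16.5.3 with 8.1.1, so that it is clear whether a value that by itself stops study drug is recorded as an adverse event.

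The cost is a few tables and some wording. The samples and laboratory results are already scheduled. The rules should be fixed before the assay results are seen.
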